Design and Setting. Utilizing clinical lab methods, this aim provides broad testing of the top 4 HWLs on a myriad of WP smokers' subjective and objective outcomes. *We will recruit 2 groups of WP smokers (124 each, total 248; age 18-29 yrs) based on their use frequency (beginners: started WP smoking in the past 6 months, but smoke WP less than weekly; established: smoked at least once a week in the past 6 months) for a 2x2x2x4 within-subject (2: HWL vs no-HWL x 2: pre- vs post- smoking) and between-subject (2: beginner vs established smokers x 4: HWLs) experimental study. Participant in each group (beginner, established smoker) will be randomly assigned to one of the 4 HWLs conditions, and undergo 2 WP smoking sessions that differ by HWL on the WP device (HWL vs. no-HWL), with pre-/post-smoking assessment of harm perception, intention to quit, puffing behavior, satisfaction, urge to smoke, and toxicant exposure (CO, nicotine, oxidative stress) (Figure 9). We will use Latin Square crossover design balanced for carry-over effect (random order of 4 HWL condition), and to ensure equal distribution of study participants across gender. Accordingly, every subject will undergo 2 WP smoking sessions in the clinical lab setting differing by label (HWL vs. no-HWL) in a balanced random sequence; the same number of subjects gets each label and its order (1st or 2nd session) the same number of times, and for each gender. As in (Evans 2015, Brewer 2016, Brewer 2019), all participants will receive a follow-up phone call assessment after 3 months of the last session to evaluate the longer-term effect of exposure to the HWLs in real-world setting including HWLs recall, social interactions about WP harms (talk about HWLs with family/friends), and behavioral adaptations in response to exposure to HWLs (e.g., harm perception, quit intention, quitting).*

Such an approach allows:

- 1- Thorough comparisons without the need for large samples using powerful within-between subjects design.
- 2- Comparative testing for HWLs with current practice (no label control).
- 3- Comparative assessment of the 4 HWLs, and the themes they represent, on important

outcomes through between-subjects pre-post analysis.

4- Assessment of the expected effect of HWLs on WP smokers at different stages of their smoking trajectory.

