Objectives and Hypotheses. To assess WP smokers' responses to the developed pictorial HWLs and inform the state of Florida about HWLs potential to curb WP use among youth in Florida. The study will examine smokers' harm perception, intention to quit, puff topography, satisfaction, dependence, and toxicants exposure (CO, nicotine, EBC oxidative stress) pre-post smoking under 2 conditions (H WL vs. no-H WL). We hypothesize that 1) HWLs on the device will reduce smoking (puffing) intensity, satisfaction, exposure to toxicants, dependence parameters and increase harm perception and intention to quit compared to no-HWL control; and 2) this effect will be more pronounced in beginning vs. established WP smokers.

Participants, Recruitment, and Procedures. As in Aim 1, in this study we will recruit WP smokers through the same online, offline and in-person recruitment methods described in section (C.2.2. Recruitment, Aim 1). Individuals who report smoking cigarettes or other tobacco/nicotine products (e.g., e-cigarettes, pipes, cigars) will be included to increase the generalizability of results, as long as they identify themselves as primarily WP tobacco smokers (do not report using cigarettes/e-cigarettes/other tobacco products regularly > 4 times/month). Concurrent regular use of other tobacco/nicotine products would bias the measurement of WP associated outcomes (e.g. dependence measures) (Ben Taleb 2018). *Participants completing the 2 lab sessions and 3-month follow-up will be compensated \$36 for each visit. Based on previous experience ([name] 2019, a), we expect to study 8-10 subjects/month. We will continue recruitment until we reach the target sample (248 with complete sessions). While recruitment is always a challenge, our lab, led by Co-PI [name] has easily recruited >150 WP users for two-session study (similar design) in the past 2 years with negligible drop out using comparable incentives ([name] 2019, a). This is due to the widespread of WP smoking among college students in Florida (up to 34%) (Martinasek 2016), especially in a large university with about 57,000 students such as FIU, where our lab is located.*

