5. Change in WP smoking will be asked at 3-month assessment using 3 items; “*Since you started the study, 1- did you stop smoking for 1 day or longer because you were trying to quit WP smoking?, 2- did you avoid smoking WP because you were thinking about the HWLs?, and 3- did you stop WP smoking completely because of the HWLs?*” (Brewer 2016).
6. Toxicant exposure includes eCO, plasma nicotine, and EBC oxidative stress.
 - eCo will be measured initially at the beginning of the smoking session (abstinence verification), and within 10 min after the WP smoking session via e-CO monitor (Vitalograph, Lenexa, KS).
 - Plasma nicotine will be assessed pre-/post-smoking. The research nurse will draw Blood samples (~ 10 ml) via a butterfly needle from a forearm vein before smoking session onset and within 10 minutes of its end. Research staff will centrifuge blood samples and freeze plasma immediately, to be analyzed later by Forensic Chemistry Lab at FIU using Liquid Chromatography Mass Spectrometry.
 - Exhaled Breath Condensate (EBC) will be collected pre-post smoking session to test for markers of oxidative stress and DNA damage. We will test for 6 biomarkers (8-oxodGuo, 8-oxoGuo, 8-isoprostanate, formaldehyde, acetaldehyd and malondialdehyde) (Gong 2013, Hu 2015). Samples will be collected during 15 min of tidal breathing through a single-use disposable RTube TM collector (Respiratory Research, Inc., Charlottesville, Va., USA). After sample collection, a plunger will be used to pool the condensed material within the tube into a single sample (about 1.0-2 ml). EBC samples will be divided in aliquots and stored at -80°C. EBC samples will be analyzed by our Forensic Chemistry Lab at FIU using Online Solid-Phase Extraction and Liquid Chromatography Triple Quadrupole Mass Spectrometry (LC-QqQ-MS) and Gas Chromatography Mass Spectrometry (GC-MS) (Hu et al., 2015; Gong et al., 2013). malondialdehyde) (Gong 2013, Hu 2015).

7. Puff topography will be assessed continuously during smoking. It will be measured with a device that was developed by Shihadeh (Shihadeh 2005b), and validated in several WP studies ([name] 2009, Cobb 2015). Briefly, a pressure transducer is integrated into the WP hose, and inhalation-induced pressure changes are amplified, digitized, and sampled at a rate of 1000 Hz. The software converts signals to airflow (ml/sec) and integrates the flow data, producing measures of puff volume, duration, number, and interpuff interval (IPI).

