8. Cardiovascular measures will be assessed continuously during smoking. Two physiological measures will be monitored during each session; heart rate and BP (systolic, diastolic, and mean arterial) using Noninvasive Patient Monitor 507E, Criticare Systems, Waukesha, WI. Physiological data transfer directly to a computer. Heart rate will be recorded every 20 seconds and blood pressure will be measured every 5 minutes before and during WP use.
9. Subjective dependence and satisfaction measures assess smoker's satisfaction with smoking, and the direct effects of tobacco/nicotine consumption on dependence measures (e.g. withdrawal and craving). We will use 4 subjective measures: The Duke Sensory Questionnaire (DSQ) (Malson 2002, Pickworth 2002); The Cigarette/WP Evaluation Scale (WES) (Rose 2000, Malson 2002); The brief version of Questionnaire of Smoking Urges-brief (QSU) (Cox 2001); and Minnesota Nicotine Withdrawal Scale (MNWS) (Hughes 1986). Participants will use a computer keyboard and mouse to respond to these measures periodically in each label condition using Survey Monkey software. The first 2 measures (DSQ, WES) will be used only after smoking, while dependence (QSU, MNWS) measures will be assessed pre-post WP smoking (Ben Taleb 2018, [name] 2019, b). Subjective measures' assessment will take place within 20 minutes before and after WP smoking.

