Statistical Analysis. Prior to analysis, physiological data will be averaged to produce a single baseline value for each measure (10 minutes prior to WP use) and for each 10- minute that a participant was actually using the WP. Topography data will be processed automatically by the topography instrument software to eliminate closely spaced puffs (i.e., IPIs < 300 msec). Such puffs are assumed to be part of the previous puff and the recorded volume and duration values will be added to that preceding puff ([name] 2009). After this procedure, any puffs less than 5 ml will be considered an artifact and automatically discarded. Remaining data will be averaged for each participant in each condition using all remaining values for puff volume, duration, number, and IPI (Shihadeh 2004). We will address the issue of stability of WP puff topography by correlating topography values across sessions (Shihadeh 2005a). For plasma nicotine, values below the limit of quantitation (LOQ) will be replaced with the value of the LOQ ([name] 2011). Demographical data will be examined to determine if there are significant between-group differences on measures that may be related to study outcome (some differences are expected due to design such as past 30-day WP use) though these are expected to be minimized as a virtue of randomization. Unexpected between-group differences will be considered as potential adjustment covariates in the primary analysis (Evans 2006). *The primary analysis of each outcome will involve a 4-factor analysis of variance (or covariance) with two within-subject factors; HWL (HWL vs. no-HWL/control) and time (pre-post smoking), and two between-subject factors; smoking frequency (beginner vs. established WP smokers) and HWL (4 group assignment). This approach will be extended into mixed-effects linear regression model in order to adjust for potential confounders such as gender, education, race, SES, and self-efficacy. To assess if gender has any effect on the results, it will be considered as a covariate and we will test the pre-planned interaction with it to determine heterogeneity of HWL by gender as well as potential differential effects.* We will test for carry over effect statistically and will control for it when testing for the primary factors (Senn 2002). Significance levels will be adjusted for violations of the sphericity assumption using Huynh-Feldt corrections (Keppel 1991). The mean square error terms for the overall interaction will be used to conduct Tukey's honestly significant difference test (Keppel 1991), with comparisons at $P < 0.05$ considered significant.

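### The pre/post four-factor ANOVA set for every outcome cannot be fitted to puffing or satisfaction, the term testing each hypothesis is not named, and the all-effects 80% power claim does not carry over to outcomes with one value per session

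*Combined protocol and SAP*

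**What the plan says.** All references are to the combined protocol and SAP, section C.5 (Aim 2).

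- **Statistical Analysis** states "The primary analysis of each outcome will involve a 4-factor analysis of variance (or covariance", closing bracket omitted here, with "two within-subject factors; HWL (HWL vs. no-HWL/control) and time (pre-post smoking), and two between-subject factors". The between-subject factors are smoking frequency and assigned label. A mixed-model extension adds covariates such as gender, education and SES. Carry-over is to be tested and controlled for. The only interaction called pre-planned is the one with gender.
- **Outcome Measures, item 7:** "Puff topography will be assessed continuously during smoking". Statistical Analysis then reduces the record: "Remaining data will be averaged for each participant in each condition using all remaining values for puff volume, duration, number, and IPI".
- **Outcome Measures, item 9:** "The first 2 measures (DSQ, WES) will be used only after smoking", "while dependence (QSU, MNWS) measures will be assessed pre-post WP smoking".
- **Design and Setting**, by contrast, promises "pre-/post-smoking assessment of harm perception, intention to quit, puffing behavior, satisfaction, urge to smoke, and toxicant exposure".
- **Objectives and Hypotheses**, hypothesis 1: "HWLs on the device will reduce smoking (puffing) intensity, satisfaction, exposure to toxicants, dependence parameters and increase harm perception and intention to quit". Hypothesis 2 expects a stronger effect in beginners than in established smokers.
- **Sample Size** claims at least 80% power with 240 people at Cohen's f = 0.2 for all within-subject, between-subject and interaction effects, with correlation 0.5 among repeated measures. The planned enrolment is 248 (124 per smoker group, 62 per label).

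**The concern.** A factor for time before versus after smoking needs both readings. Puffing and satisfaction have one value per session, so the prescribed model does not exist for two outcome families in hypothesis 1. The Design and Setting paragraph says the opposite of the measurement schedule.

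Where both readings exist, the wording of the objectives points towards HWL × time, but an adjusted comparison of post-smoking values would be equally natural. The two can disagree if the label's effect persists into the second session, and the term could be chosen after the data are seen.

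The power sentence is written for the four-reading layout and for all effects, yet it is offered for the whole study.

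**Working it through.** **1. Can the model be fitted?** With time held at one level, the design matrix for HWL × time × smoker group has rank 4 out of 8 columns. Time and all its interactions are inestimable. HWL, smoker group and HWL × group remain.

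**2. The plan's own power figure.** Inputs from Sample Size: N = 240, f = 0.2, ρ = 0.5, α = 0.05, 2 × 4 = 8 between-subject cells. For a between-subject effect with m readings per person, the noncentrality is λ = f²·N·m / (1 + (m − 1)ρ), with N − 8 error degrees of freedom. The plan does not say which effect limits power; the 7-df comparison of all eight cells is the one that reproduces its figure.

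- m = 4: λ = 0.04 × 240 × 4 / 2.5 = 15.36; F(7, 232); power **81.8%**. The claim is met.
- m = 2 (one value per session): λ = 0.04 × 240 × 2 / 1.5 = 12.80; F(7, 232); power **72.8%**. At N = 248, λ = 13.23 and power is **74.5%**. Reaching 80% would take 277.
- m = 2, 3-df label effect, N = 240: power 85.9%.
- Within-subject effects and their interactions at f = 0.2 stay above 99% with either m.

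**3. Hypothesis 1.** Assume the pilot f = 0.19 means a label effect of 2 × 0.19 = 0.38 SD. Let D be the label-minus-control difference: Var(D) = 2(1 − 0.5) = 1 in SD² units. The noisiest candidate, HWL × time with all correlations 0.5, has SE √(2/248) = 0.090, so 0.38/0.090 = 4.23 and power is about 0.99. At correlation 0.3 it is still about 94%.

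**4. Hypothesis 2: gap between smoker groups detectable with 80% power.** Multiply the SE by 2.80.

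- One value per session: 2.80 × √(2/124) = **0.36 SD** (0.28 to 0.42 SD for correlation 0.7 to 0.3).
- Through time with equal variances: 2.80 × √(4(1 − r)/124), where r is the correlation between the pre-smoking and post-smoking between-session differences. This gives **0.50 SD** at r = 0, **0.44 SD** at r = 0.25 and **0.36 SD** at r = 0.5. The plan's single common correlation implies r = 0.
- On the f scale, 0.2 corresponds to 4f = 0.8 SD for HWL × group and 8f = 1.6 SD with time added, so the design detects smaller gaps than f = 0.2 conveys.

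**5. What baseline adjustment gains.** The variance of HWL × time relative to the adjusted post-smoking contrast is 2(1 − r)/(1 − r²) = 2/(1 + r) with equal variances: 2.0 at r = 0 and 1.33 at r = 0.5. For eCO the pre-smoking value is held near or below 5 ppm by the abstinence check. With an assumed pre-to-post SD ratio k of 0.07 to 0.20 and r of 0 to 0.5, (1 + k² − 2rk)/(1 − r²) is only about 1.0 to 1.25. Through-time power for a 0.38 SD gap (post-smoking SD) is then about 83% to 90%.

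**6. Does the choice of term matter?** Illustrative simulation: 2,000 runs, N = 248, all correlations 0.5, true effect 0.38 SD, carry-over only when the label comes first. The carry-over sizes are invented for illustration.

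| Carry-over into session 2 | Adjusted post | HWL × time |
|---|---|---|
| 0.2 SD in both readings | 0.28 | 0.38 |
| 0.2 SD before, 0.1 SD after smoking | 0.33 | 0.43 |
| 0.2 SD after smoking only | 0.28 | 0.28 |

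A session-1-only estimate stays at 0.38 but has SE √(0.75 × 2/124) = 0.11.

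**The case against.** The strongest reply is that the first defect repairs itself. With one value per condition, time drops out and HWL and HWL × group are the only terms left, so there is no real freedom of choice for puffing and satisfaction. Item 9 is explicit about timing, and Design and Setting is a loose summary. That is fair on consequence. It does not change the fact that the plan prescribes a model for each outcome that two families cannot have, and that two paragraphs conflict.

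The plan also already promises to test and control for carry-over. That stands, but it does not say how, or in which term, so it does not settle the choice in step 6.

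A reader might infer that f = 0.2 leaves hypothesis 2 able to detect only gaps of 0.8 or 1.6 SD, or that its power is 56% for a gap as large as the pilot effect and 18% for half of it. The documents support neither. The detectable gaps are well below 0.8 SD. The 56% and 18% arise only for equal variances and r = 0; at r = 0.5 the power for a 0.38 SD gap is 85%. They should not be attached to eCO, the outcome on which the pilot effect was measured.

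**Conclusion.** The point holds as a specification gap. The primary model is inestimable for topography, DSQ and WES. The testing terms for both hypotheses are unnamed, and the session's pre-smoking value is not used as a covariate.

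The power statement contains no arithmetic error, but its all-effects scope fails for outcomes with one value per session: 72.8% at 240 and 74.5% at 248 for the eight-cell comparison. A reader might infer an underpowered trial. That does not follow: neither hypothesis rests on that comparison, the label effect keeps 86%, and hypothesis 1 is safe under every term considered.

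The power recalculation uses the plan's f, α and correlation, plus the inferred 7-df limiting effect. The SD-scale results also assume the 0.38 SD reading of the pilot and the stated values of r and k.

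**What to change.** 1. **Topography, DSQ, WES:** drop time. Fit HWL, period, sequence, smoker group, label, HWL × group and HWL × label. Name HWL as the test of hypothesis 1 and HWL × group as the test of hypothesis 2. Reconcile Design and Setting with Outcome Measures and Statistical Analysis.
2. **eCO, nicotine, EBC markers:** model the post-smoking value with the same terms, plus the session's pre-smoking value and the person's mean pre-smoking value. The testing terms are the same. Expect little gain for eCO.
3. **Harm perception, quit intention, QSU, MNWS:** name HWL × time (hypothesis 1) and HWL × time × group (hypothesis 2) in advance. Give adjusted-post and session-1-only estimates as sensitivity analyses, and tie them to the existing carry-over provision.
4. **Power sentence:** restrict the 80% at f = 0.2 claim to outcomes with four values per person. For one-value-per-session outcomes, state about 73% at 240 (75% at 248) for the all-effects figure. Enrolling more is not warranted.
5. **Optional:** report the hypothesis 2 detectable gap from step 4 of the working, with its dependence on the correlation and r stated.

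The cost is SAP wording and some extra analysis; every measurement is already planned. The downside is that item 3 is a trade-off: no two-session estimate is right under every carry-over pattern, and the session-1-only estimate is less precise.

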Inclusion Criteria. Participants need to be generally healthy (at a screening physical examination), between the ages of 21-35 years, willing to provide written informed consent, attend the lab as required, abstain from WP or any tobacco/nicotine for ≥ 12 h prior to study verified by expired air carbon monoxide eCO<5 ppm (Ben Taleb 2018), and use a WP to smoke tobacco in the lab according to study protocol. The 12 hour abstinence period is needed to clear plasma nicotine from prior-to-study smoking (6-8 h after cessation is needed to clear plasma nicotine) (Benowitz 2009) and ensure that all study measures are influenced mainly by study conditions. *Self-reported WP use will be used to define 2 groups of WP smokers (beginners, established), which mostly reflects smokers at different stages of their WP use trajectory ([name] 2016). These are consistent with common WP use patterns among young people in the US, and our previous lab studies with WP smokers, which will enhance recruitment and generalizability of our results (Primack 2013, Haider 2015).*

Exclusion Criteria. As is standard for clinical lab studies involving smoking, safety concerns require that individuals with self-reported history of chronic disease, psychiatric conditions, history of cardiovascular disease, low or high blood pressure (BP) (systolic BP>150 mm Hg, or diastolic BP>100 mm Hg), seizures, or regular use of prescription medications (other than vitamins or birth control) be excluded (Ben Taleb 2018). Women will be excluded if they are breast-feeding or test positive for pregnancy (by urinalysis) at screening. Individuals who fail the eCO test may be rescheduled at another date.

Sample Size. We built our calculation of the sample size for this study on eCO differences in our HWL pilot study (pls. see preliminary studies C.1.2. and Figure 6), which reported a small-

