Experimental Methods. Participants will be randomly assigned to one of the 4 HWLs conditions and attend the lab for two, ~2-h sessions, separated by a 48-h washout period, and differ by HWL on the device (H WL vs. no-HWL control). Session order will be randomly counterbalanced to avoid order effects; counterbalancing also will allow us to study the effect of HWL on smoking behavior prospectively (i.e. between sessions difference is expected to be less when the HWL condition is tested first). They will also be balanced across the 4 HWLs (62 sessions for each HWL) to allow for equal numbers and robust comparisons of the 4 HWLs and their representative themes.

At the beginning of the 1st session, participants will provide demographic and personal information including age, socioeconomic status, race/ethnicity, and detailed tobacco use history, especially WP use. Then abstinence will be verified by eCO<5 ppm. Those who have eCO>5 ppm will be rescheduled. Those who are abstinent will get familiarized with the study procedures, measures, and they will be given time to adapt to the lab.

After adaptation, continuous measurement of physiological responses begins, and 10 ml of venous blood is sampled, and participants are asked to respond to subjective measures (pls. see below Outcome Measures). They will then begin a maximum 45 min WP smoking session (time recorded) using a device fitted with the pre-selected HWL or no-HWL according to condition. The HWL will be placed in a constant location/size on the device, which will be placed in front of participant seat (at vision level). For each participant, preferred brand/flavor of WP tobacco (verified at screening) will be used to neutralize the effect of nicotine/flavor on study outcomes. We will follow our tested lab protocol developed to study the WP (Ben Taleb 2018), where prior to each session, the lab staff will pack the WP head with 15 g of the participant's favorite tobacco preparation and cover it with perforated foil. Tobacco will be heated with quick-light charcoal disks (33 mm diameter; 6.2 g; Three Kings, Holland, or similar brand). Initially, a single charcoal disk will be used, and several (pre-weighed) ½ charcoal disks will be made available to the participants so they can add *ad libitum* (Cobb 2012). The timing of each

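### The promise to test and control for carry-over names no method, and in this two-session crossover both ways of acting on it do worse than a fixed two-session model with a session 1 sensitivity analysis

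*Combined protocol and SAP*

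**What the plan says.** Under C.5 Aim 2, Design and Setting, every participant is assigned one of four labels and smokes twice, once with it and once without, in balanced order. Experimental Methods has participants "attend the lab for two, ~2-h sessions, separated by a 48-h washout period". The same section adds that "counterbalancing also will allow us to study the effect of HWL on smoking behavior prospectively", because the "between sessions difference is expected to be less when the HWL condition is tested first". So the protocol itself expects the label to carry over to the next session.

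The Statistical Analysis section names a four-factor model: label presence and time within subject, smoking frequency and label group between subjects. It then says: "This approach will be extended into mixed-effects linear regression model in order to adjust for potential confounders", and lists participant characteristics. Neither model names session, sequence or carry-over. The rule itself is one sentence, "We will test for carry over effect statistically and will control for it when testing for the primary factors", with a general crossover text as reference. It gives no contrast, level, outcome list or action on a positive result.

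Under Outcome Measures, DSQ and WES are taken only after smoking, and topography only during it. Pre-smoking eCO is an abstinence check that must be below 5 ppm, and the procedure is repeated in session 2. On the sample size, the plan says: "We built our calculation of the sample size for this study on eCO differences in our HWL pilot study".

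**The concern.** A two-session, two-order crossover yields four cell means (order by session). A model with a mean, a label effect, a session effect and a sequence effect uses all four, so nothing is left to estimate carry-over. Where the pre-smoking value can show persistence (harm perception, quit intention, QSU, MNWS), there is extra information. Topography, DSQ and WES have no such value. For eCO, and plausibly plasma nicotine after 12 hours' abstinence, it is held low by design.

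For those outcomes the sentence can be carried out in more than one way, and the choice changes precision, type I error or both. An analyst could choose after seeing the data. At stake are the size and interval of the label effect, including on the outcome behind the sample size, and the contrasts between labels and between beginner and established smokers.

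**Working it through.** **Inputs.** From Sample Size: 248 participants, correlation ρ = 0.5, α = 0.05, pilot f = 0.19. Balanced order gives 124 per order. Assumption: d = 2f = 0.38 SD. The documents give no size for carry-over, so I write it as λ = c × 0.38 SD and vary c.

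**The plan's own figure.** It claims at least 80% power with 240 participants at f = 0.2. Taking the between-subject effect with 8 cells and 4 measures, the noncentrality is 0.04 × 240 × 4 / (1 + 3 × 0.5) = 15.36 on 7 and 232 df. Power is 81.8%, so the figure reproduces. It allows nothing for carry-over adjustment.

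**What can be estimated.** Let τ be the label effect, π the session 2 drift, and λ the carry-over from HWL into a later no-HWL session.

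- HWL first: means μ + τ, then μ + π + λ.
- No-HWL first: means μ, then μ + π + τ.
- With μ, π, τ and λ all fitted, τ has weights (+1, 0, −1, 0) on these four means. That is exactly the session 1 contrast.
- Adding a sequence effect leaves rank 4 for 5 parameters, so λ and sequence are aliased.

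**Cost of always controlling.**

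- Two-session variance: 2(1 − 0.5)/248 = 0.00403 (SE 0.0635).
- Session 1 only: 2/124 = 0.01613 (SE 0.127).
- Ratio: 4.0 (2.9 at ρ = 0.3, 6.7 at ρ = 0.7).
- With π set to zero, label and carry-over can be fitted together. SE is 0.084 (ratio 1.75), or 0.090 (ratio 2.0) with a sequence term.

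Session 1 power at 0.38 SD is 85% pooled (124 vs 124) and 31% for one label (31 vs 31). For a beginner-versus-established difference of 0.38 SD it is 32%, against 85% using both sessions.

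**Cost of testing first.** The standard test compares two-session sums between orders. Its SE is √(2 × 2(1 + 0.5)/124) = 0.220. For c = 25/50/100%, power is 7/14/41%. Suppose a significant result sends the analysis to session 1. With no true effect and no carry-over, the carry-over statistic is independent of the two-session statistic, but has correlation √((1 + ρ)/2) = 0.866 with the session 1 statistic. Type I error is then:

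- pre-test at 0.05: 0.95 × 0.05 + 0.0266 = 7.4%
- pre-test at 0.10: 0.90 × 0.05 + 0.0370 = 8.2%

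Across ρ of 0.3 to 0.7 and both levels the range is 7.0% to 8.8%.

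**The order comparison in Experimental Methods.** HWL minus no-HWL has expectation τ − π − λ when HWL is first and τ + π when it is second. The orders therefore differ by λ + 2π, with SE √(2 × 2(1 − 0.5)/124) = 0.127. With no carry-over, a drift of 0.1 SD is significant 35% of the time (26% to 53% for ρ of 0.3 to 0.7). With λ = 0.19 and drift of −0.1, the expectation is −0.01 and power is 5%. Drift can mimic carry-over or hide it.

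**If carry-over is ignored.** The two-session estimate averages the two orders: τ − λ/2, with or without session and sequence terms. As an illustration, c = 25/50/100% gives bias of 12.5/25/50% of the effect and 95% interval coverage of 88/68/15%.

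**The case against.** The plan does more than stay silent. It balances order, sets a washout and describes an order comparison, and it treats persistence partly as something to study. Its wording reads most naturally as unconditional control, under which type I error stays at 5%. The cited crossover text may fix a procedure. These points stand in part: the 7.4% to 8.2% applies only if control depends on the test, which the sentence leaves open. A general reference does not by itself select a method.

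A reader might infer that session 1 is the only way to control for carry-over here. That needs a session effect in the model. Without one, two-session estimates remain possible at 1.75 to 2.0 times the variance. The plan neither states nor justifies that assumption.

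A reader might also infer that uncorrected results must be conservative. That holds only if carry-over has the sign of the label effect. Experimental Methods expects this for smoking behavior, but as an expectation. With c = −50%, the estimate would be 25% too large.

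Finally, the fix leaves carry-over in the primary estimate. This is true, and it is a deliberate trade. At ρ = 0.5 the two-session estimate has lower mean squared error than session 1 until (0.19c)² + 0.00403 = 0.01613, that is c of about 58% (54% to 62% for ρ of 0.3 to 0.7).

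**Conclusion.** The concern holds in this form. The sentence commits to acting on carry-over in a design that supports this poorly for topography, DSQ, WES and, plausibly, eCO and plasma nicotine. Always adjusting with a session term multiplies the variance by 4 at ρ = 0.5. Adjusting after a test raises type I error to about 7.4% to 8.2% and relies on a test with about 14% power for carry-over of half the effect.

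The documents do not support reading this as a threat to the pooled label test. Even at c = 100% the two-session comparison keeps about 85% power at ρ = 0.5 (71% at ρ = 0.3). The harm is to effect size, interval coverage and HWL-by-label contrasts. Label comparisons within the HWL session alone, one reading of "outcomes through between-subjects pre-post analysis", do not use the contaminated session.

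The figures rest on d = 2f, equal variances, 124 per order and the stated correlation. The amount of carry-over is unknown, so the bias and coverage figures are illustrations. This should be fixed, but it does not undermine the trial.

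**What to change.** In C.5 Aim 2, Statistical Analysis:

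1. Replace the test-and-control sentence. State that no carry-over test chooses or adjusts the primary analysis, and that any such test, including the comparison by order, is reported descriptively and not read as carry-over alone.
2. Add session and sequence terms to the two-session within-subject model and name it as the primary estimator, using HWL-by-time where a usable pre-smoking value exists. Classify the EBC and cardiovascular outcomes on this point before analysis.
3. For the affected outcomes, always report the pooled session 1 comparison (124 vs 124) as a pre-specified sensitivity analysis that never replaces the primary estimate.
4. State that the primary estimate is still biased by half of any carry-over: towards zero if carry-over has the sign of the label effect, away from zero otherwise. State that HWL-by-label contrasts share this limit.

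The cost is SAP wording and one extra model per affected outcome, with no new data. The downside is that any carry-over stays in the primary estimate, and the session 1 check is informative only for the pooled effect.
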